Officer for Nemours Children's Health System; **2) [name], MPH**, Director of the Christiana Care Harrington Value Institute Community Partnership Fund and Harrington Trust Physician Scholar; **3) [name]**, Director of the University of Delaware (UD) Partnership for Healthy Communities and Professor of Practice and Distinguished Health and Social Services Administrator; and **4) [name]**, Attending Physician in the Nemours Division of Infectious Disease to provide expertise on the public health response to the pandemic. Finally, this project leverages robust resources offered by the Nemours Primary Care Network (Director **[name]**, co-investigator), and the Nemours Office of Health Equity and Inclusion (Research Associate **[name], BSPH, MPH**, co-investigator). Nemours Marketing and Center for Health Delivery Innovation (CHDI) will help create intervention prototypes and final intervention components.

C3. PARTNER ENGAGEMENT PLAN. To create a culturally-tailored and community-informed intervention, community and healthcare stakeholders (Table 2) will be engaged as research partners. Identification and engagement of partners will be facilitated by the UD Partnership for Healthy Communities ([name]) and Harrington Value Institute Community Partnership Fund ([name]). This Council of Community and Healthcare Partners will meet regularly throughout the course of the study with our team of investigators. Best practices from the Promising Practices Guide developed by the University of New Mexico's Engage for Equity team will be followed to ensure that community partner engagement is successful.¹⁷⁻²⁰ In addition, three FYREworks training modules²¹ (30 minutes each) will be completed by all community and healthcare partners prior to the first meeting to foster an understanding of their role in the research process.^{18,20} The quality of the research partnership will be evaluated using Engage for Equity's Community Engagement Survey²⁰ following every meeting to ensure partner synergy and alignment of values, modifying our community engagement practices as needed based on responses.

C4. STUDY DESIGN. Please see PHS Human Subjects & Clinical Trials form for detailed eligibility criteria, sample size justification, recruitment/retention plan, timeline, human subjects protection, participant compensation, and data/safety monitoring.

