INTERVENTION REFINEMENT: Ratings on the AIM range from 1 to 5, with higher scores indicating greater acceptability. A score of 4 indicates that participants "agree" that interventions are acceptable. Intervention components with a mean score < 4 will be modified based on qualitative responses, with the research team determining what modification can be made based on importance and feasibility. The process of revision and participant feedback will continue until the mean acceptability score is ≥ 4 .

AIM 3. Test the preliminary efficacy of the intervention through a pilot cluster randomized controlled trial of the intervention at 4 Nemours primary care sites.

[figure not shown]
PARTICIPANTS: Four primary care practices will be enrolled in the study (Figure 4), leveraging RPL [name]'s prior work with primary care practices in Delaware and co-I's [name] role as Director of the Nemours Primary Care Network. The four primary care practices selected for the study have large and diverse patient populations, with two practices in Northern Delaware (Becks Woods, Foulk Road) and two in Southern Delaware (Milford, Seaford) having comparable patient demographics. All practices are within the Nemours Children's Health System, which provides care to the majority of children in the state, and share an EHR.

STUDY DESIGN: A pilot cluster randomized controlled trial will be conducted, with clustering at the practice level. Enrolled practices will be randomly allocated to receive the intervention (Intervention Practice) or not (Control Practice) using a 1:1 randomization scheme stratified by practice location (Northern or Southern Delaware).

OUTCOME MEASURES

Vaccination Rates: We will extract EHR data about rate of COVID-19 vaccination for all eligible children at each practice.

Accountability for Vaccination: Vaccination rates for each site will be made available and reviewed monthly by the Nemours Primary Care

Network, who will share an overview of de-identified data with the Delaware Division of Public Health and partner with them to ensure that enough COVID-19 vaccines will be allocated and distributed to communities to meet demand and that continual efforts to encourage vaccination.

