Disparities: Child race/ethnicity (Black, White, Latino, Other) will be the primary measure of disparity and will be collected from the EHR. Zipcode from the EHR will be used to categorize patients into rural vs. not (RUCA ≥4)⁴⁰ and to generate a Child Opportunity Index score⁴¹ for each child as secondary measures of disparity. Insurance, sex, medical diagnoses, and caregiver preferred language will also be collected from the EHR.

ANALYSES: Analyses demonstrated the efficiency of the stratified cluster randomized trial in detecting a difference in vaccination rate of 30% among Blacks in the Control Practices compared to an increase in vaccination rate to 60% among Blacks in Intervention Practices, with a sample size of 500, $\alpha < 0.05$ and power of 90%. Proportions of caregivers who vaccinate their child will be compared by level of intervention using chi-square tests. To test the efficacy of the intervention, while accommodating the cluster-randomized design of the study, a multi-level mixed-effects model (MME) logistic regression will be used fit to the data for the primary outcome of child vaccination rate to assess the effect of intervention. MME models will be adjusted for race/ethnicity to evaluate the effect of intervention on reducing this disparity.

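### The efficacy test rests on four practices and no small-sample reference is named, so the usual normal-based inference does not assure the 5% level, and the 90% power claim needs restating

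*Combined protocol and SAP*

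**What the plan says.** All references are to the Combined protocol and SAP, section C4, unless noted.

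- **Aim.** "Test the preliminary efficacy of the intervention through a pilot cluster randomized controlled trial of the intervention at 4 Nemours primary care sites".
- **Clusters and allocation.** "Four primary care practices will be enrolled in the study", allocated "using a 1:1 randomization scheme stratified by practice location (Northern or Southern Delaware". Each arm therefore has one northern and one southern practice. The Participants paragraph lists two northern practices and "two in Southern Delaware (Milford, Seaford) having comparable patient demographics".
- **Efficacy test (Analyses).** "a multi-level mixed-effects model (MME) logistic regression will be used fit to the data for the primary outcome of child vaccination rate". Race/ethnicity is the only adjustment named. No estimation method, reference distribution, degrees of freedom, permutation test or practice-level test is given. A chi-square comparison is also listed, but it takes no account of clustering and so supplies no remedy.
- **Power (Analyses).** 30% in control practices "compared to an increase in vaccination rate to 60% among Blacks in Intervention Practices, with a sample size of 500", alpha 0.05 and 90% power. No ICC or design effect is stated.
- **Data.** "We will extract EHR data about rate of COVID-19 vaccination for all eligible children at each practice", so practices may contribute more than 125 children each, and unequal numbers.
- **Elsewhere.** Section C4 opens by referring to a separate "form for detailed eligibility criteria, sample size justification, recruitment/retention plan, timeline, human subjects protection". That form is not among the documents. It may hold an ICC, but the items it is cited for do not include the analysis method.

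**The concern.** The intervention is assigned to practices, so the error in the arm comparison is the variation between practices. With two practices per arm, that variation is estimated on 2 degrees of freedom. Wald z (1.96) and the likelihood-ratio test (chi-square, 1 df) treat it as well estimated, whereas the two-sided 5% critical value of t on 2 df is 4.30. In addition, maximum likelihood often sets so poorly estimated a variance to exactly zero, and the model then behaves as if children were independent.

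At stake is whether the reported p-value and interval can be taken at face value. Section C7 intends the result as preliminary evidence of efficacy in support of funding for a larger trial.

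**Working it through.** **1. The plan's own figure.** For 30% against 60%, two-sided alpha 0.05 (sidedness is not stated) and 90% power, with no clustering:

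n per arm = [1.96·√(2·0.45·0.55) + 1.2816·√(0.3·0.7 + 0.6·0.4)]² / 0.30² = 55.7, so 56 per arm and 112 in all.

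Without clustering, 250 per arm would give more than 99.9% power. N = 500 gives 90% under a normal reference only with a design effect of 250/55.7 = 4.49, that is ICC = (4.49 − 1)/124 = 0.028 at 125 per practice. The documents do not state this value. It is an illustration, and applies only if the whole excess over 112 is a clustering allowance.

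**2. Type I error of the stated model under normal-based inference.** From the documents: four practices, two per arm, one per region in each arm, 30% vaccinated. Assumed: 500/4 = 125 per practice, latent ICC = σ²/(σ² + π²/3) of 0 to 0.05, maximum likelihood, nominal two-sided 5%. Random-intercept logistic model, 6,000 simulated trials per cell (3,000 when race-adjusted), no regional gap:

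| Latent ICC | 0 | 0.01 | 0.03 | 0.05 |
|---|---|---|---|---|
| Wald z | 4.5% | 11.6% | 20.4% | 23.3% |
| Wald z, race-adjusted | 5.0% | 12.9% | 20.7% | 25.0% |
| Likelihood-ratio | 3.7% | 8.7% | 15.4% | 17.0% |
| Likelihood-ratio, race-adjusted | 3.9% | 9.4% | 14.9% | 18.6% |

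The fitted practice variance is exactly zero in 66 / 42 / 32% of trials at ICC 0.01 / 0.03 / 0.05. At ICC 0.03 the mean model SE is 0.27 against a true SD of 0.37, and the 95% interval covers 79.6%. With an assumed 1,000 per practice, Wald z rejects 25.9 / 28.5 / 28.9%.

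**3. Effect of a North/South gap.** The gap is not given. Centred on 30%, a gap of 0.6 logit is about 24% against 37%, and 1.0 logit about 21% against 41%. Wald z at 125 per practice, ICC 0.01 / 0.03 / 0.05:

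| Gap (logit) | Location omitted | Location fitted |
|---|---|---|
| 0 | 11.6 / 20.4 / 23.3% | 13.6 / 26.1 / 32.1% |
| 0.3 | 9.9 / 17.9 / 21.6% | not run |
| 0.6 | 4.7 / 10.4 / 14.8% | not run |
| 1.0 | 0.4 / 3.4 / 6.6% | 13.8 / 25.8 / 32.0% |

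The location-fitted column uses a normal random-effects model on practice logits; the matching likelihood-ratio figures are about 12-28%. Omitting location lets the gap inflate the fitted practice variance. Fitting it leaves 1 df for that variance.

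**4. Practice-level t.** Let l be each practice's log-odds and d the difference in arm means. Unstratified: SE = √[(s²_int + s²_ctl)/2], 2 df, critical value 4.30. Paired by location: SE = |d_N − d_S|/2, 1 df, critical value 12.71. At 125 per practice (200,000 trials per cell):

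- Level on 2 df: 4.8-5.1% with no gap, 0.5-2.3% at 0.6 logit, at most 0.6% at 1.0 logit.
- Level on 1 df: 4.8-5.2% at every gap from 0 to 1.0 logit.
- Power for 30% against 60% on 2 df, latent ICC 0.01 / 0.03 / 0.05: 69 / 45 / 34% with no gap, 50 / 37 / 29% at 0.3, 17 / 19 / 18% at 0.6, 1 / 4 / 6% at 1.0. On 1 df: about 29 / 21 / 17% whatever the gap.

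**5. The stated power under a practice-level t.** Reading 500 as the total, with no gap: SE² = (0.3·0.7 + 0.6·0.4)/250 × (1 + 124·ICC), ICC on the proportion scale, and non-centrality 0.30/SE. At ICC 0, SE = 0.0424 and the non-centrality is 7.07.

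| Proportion-scale ICC | 0 | 0.00067 | 0.01 | 0.028 | 0.05 |
|---|---|---|---|---|---|
| 2 df | 91.7% | 90.0% | 68.0% | 44.9% | 32.3% |
| 1 df | 42.1% | 40.6% | 28.9% | 20.7% | 16.4% |

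Latent ICC 0.01-0.05 corresponds to about 0.007-0.035 on the proportion scale at 30%.

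**The case against.** **The plan names a model, not a test.** It specifies neither Wald z nor the likelihood-ratio test, and the ICC, regional gap and practice sizes above are assumed. This stands. A reader might infer that the planned test has a false-positive rate of 12-25%; the documents do not support that. They support the weaker statement that the level is not assured, because the plan leaves the reference open and the usual choices depend on quantities it does not give.

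**The test may be conservative.** It may, but only if the regions differ enough and location is left out. The Analyses paragraph names only race/ethnicity as an adjustment, yet also calls the design stratified, so location might be fitted. Neither a conservative reading nor a ceiling near 29% (the largest value found with location omitted) can be relied on.

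**The 90% power is judged against a test that the plan did not propose.** A reader might infer that the figure is simply wrong. That goes too far: the separate form may state an ICC or a different size. With 500 children per practice and a proportion-scale ICC of 0.005, the 2-df formula gives 94%. What stands is that, with 500 as the total, 90% is not attainable on a valid practice-level t unless practices barely differ.

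**The remedy has limits.** This also stands. Which t analysis is better depends on the unknown gap: at 1.0 logit and latent ICC 0.01, power is about 1% on 2 df against 29% on 1 df, and with no gap the order reverses. With 25 children per practice in one arm and 225 in the other, the 2-df test rejects about 7.5% at ICC 0 and 6% at 0.01.

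**It is only a pilot.** True, and this limits the harm. Even so, the plan sets out a formal efficacy test with an alpha and a power.

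**Conclusion.** The point holds. With four practices and no stated small-sample reference, normal-based inference from the mixed model does not assure 5%. With no regional gap, 125 children per practice and latent ICC 0.01-0.05, it rejects about 12-25% (Wald z) or 9-19% (likelihood-ratio). The direction can change: about nominal or slightly below at ICC 0, possibly conservative if the regions differ and location is omitted, and inflated at both gaps examined (0 and 1.0 logit) if location is fitted. The power conclusion depends on reading 500 as the total with equal practice sizes.

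A reader might go further and expect a wrong decision to follow. The documents set no go/no-go rule on significance, so the consequence is an interval and a power claim that say more than four practices can support. It should be corrected, but it does not undermine the pilot. The point concerns the overall intervention effect, not how a change in the race/ethnicity disparity is tested.

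**What to change.** In section C4, Aim 3, Analyses, before outcomes are seen:

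1. State that the intervention effect, its 95% interval and p-value come from comparing the four practices' race/ethnicity-adjusted log-odds of vaccination by arm, with a t reference. Choose one version in advance, from what is known about North/South differences:
   - unstratified on 2 df (critical value 4.30): conservative and low-powered if the regions differ, and able to exceed 5% slightly if the arms differ greatly in practice size; or
   - paired by location on 1 df (12.71): about 5% whatever the gap, with very wide intervals.

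   The other may be reported as a sensitivity analysis.
2. Keep the mixed model as description and report its ICC, noting that a zero estimate is common with four practices. Make no significance claim from Wald z or likelihood-ratio tests.
3. Present the result as a preliminary estimate with its interval.
4. Restate the 90% power for the chosen t analysis at an explicit ICC and number of children per practice, using the separate form's values if it has them.

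Two apparent shortcuts do not work. Referring the mixed-model Wald statistic to t on 2 df gives 0.05 / 1.1 / 2.2% at 125 per practice but 4.6 / 7.1 / 7.6% at 1,000 (latent ICC 0.01 / 0.03 / 0.05). A permutation test has only 2 × 2 = 4 stratified allocations, so its smallest two-sided p-value is 0.5.

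**Cost.** Wording and a recalculation; no new data. With no regional gap, the median 95% half-width is about 1.0-1.6 log-odds on 2 df and 2.3-4.0 on 1 df, against a target effect of ln(0.6/0.4) − ln(0.3/0.7) = 1.25, and the restated power will be less favourable.

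### Adjusting for race/ethnicity cannot show whether the intervention narrowed the disparity; a secondary intervention-by-race/ethnicity model is needed

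*Combined protocol and SAP*

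**What the plan says.** All of this is in section C4, Aim 3.

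- **Disparities:** "Child race/ethnicity (Black, White, Latino, Other) will be the primary measure of disparity".
- **ANALYSES, primary model:** a multi-level mixed-effects logistic regression for the "primary outcome of child vaccination rate to assess the effect of intervention".
- **ANALYSES, disparity:** "MME models will be adjusted for race/ethnicity to evaluate the effect of intervention on reducing this disparity".
- **ANALYSES, sample size:** the calculation concerns "detecting a difference in vaccination rate of 30% among Blacks in the Control Practices", set against 60% for the same group under the intervention; it gives 500 children and 90% power. This compares arms within one racial group.
- **PARTICIPANTS and Vaccination Rates:** "Four primary care practices will be enrolled in the study", and "We will extract EHR data about rate of COVID-19 vaccination for all eligible children at each practice".

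The chi-square comparison in the same paragraph is by intervention only. No section names an intervention-by-race/ethnicity interaction, race-specific intervention effects in the analysis, or a comparison of the gap between arms. The opening of C4 refers to a separate form for several items, including the sample size justification, but does not list statistical analysis among them.

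**The concern.** To say that an intervention reduces a disparity is to say that the gap between groups is smaller in the intervention arm than in the control arm. That is a difference in effect between groups. Adjustment assumes that difference away on the log-odds scale, so the stated model does not match its stated purpose.

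Race/ethnicity is the plan's main disparity measure, and this sentence is the only analysis offered for it. If followed literally, a positive adjusted intervention effect could be reported as a narrowed disparity when the gap had stayed the same or widened. Section C7 intends the results to support a larger trial with equitable allocation as its primary outcome, so the error would carry forward.

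**Working it through.** **The plan's own figure.** No figure is given for the disparity analysis. The one stated (500 children, 30% versus 60%, 90% power) is for Black children. A standard two-sided 5% two-proportion calculation gives 56 per arm, 112 in total, without clustering. Reaching 500 needs an unstated design effect of about 500/112 = 4.5. That question is separate and does not affect this point.

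**Why the model cannot see the gap.** For child i in practice j, with arm T, race indicator R and practice intercept u:

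logit P(y_ij = 1) = a + b·T_j + c·R_ij + u_j

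Given u, the outcomes enter the log-likelihood only through Σ y_ij(a + b·T_j + c·R_ij + u_j), that is, through each practice's total vaccinated and each race group's total vaccinated. Two data sets of the same design that share those totals give the same fit, whatever the gap in each arm.

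**Check 1: equal mix.** Inputs: the plan's Black rates in Case I. The White rates, all of Case II and 125 children per cell (500 in all) are assumed. Fits use expected counts.

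| | Control White / Black | Intervention White / Black | Gap, control to intervention |
|---|---|---|---|
| Case I | 50% / 30% | 60% / 60% | 20 to 0 points |
| Case II | 40% / 40% | 70% / 50% | 0 to 20 points |

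The totals agree: 100 vaccinated in control and 150 in intervention; 137.5 White and 112.5 Black. Both cases give fitted rates of 45% / 35% in control and 65% / 55% in intervention, so:

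- intervention OR = (0.65/0.35)/(0.45/0.55) = 2.27
- race OR = (0.35/0.65)/(0.45/0.55) = 0.66
- fitted gap = 10 points in both arms, in both cases.

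The interaction odds ratio (Black intervention OR divided by White intervention OR) separates them:

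- Case I: 3.50/1.50 = 2.33
- Case II: 1.50/3.50 = 0.43.

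**Check 2: unequal mix.** 190 White and 60 Black per arm, close to the White:Black ratio of caregivers in Table 1 (869:270, or 3.2).

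- Vaccinated 95/18 in control and 114/36 in intervention (White/Black): gap 20 to 0 points.
- Vaccinated 83/30 and 126/24: gap -6 to 26 points.

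Both give an intervention OR of 1.83 and a race OR of 0.66.

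**Check 3: practice random intercept.** Four practices of 100 White and 100 Black children (assumed). The starting counts vaccinated (White, Black) are (45,25) and (55,35) in control, and (52,52) and (68,68) in intervention. Next, 5 and then 10 vaccinated children per practice are moved between race groups: White to Black in control, Black to White in intervention. The gaps are then 20 to 0, 10 to 10 and 0 to 20 points. All three fits give an intervention OR of 2.30, a race OR of 0.65, a practice SD of 0.24 and a log-likelihood of -531.353.

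**Precision of the contrast that is needed.** For the between-arm difference in gaps with the Case I rates, the sampling variance is

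(0.25 + 0.21 + 0.24 + 0.24)/125 = 0.00752.

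If the gap varies between practices with SD τ, two practices per arm add τ²/2 + τ²/2 = τ². So SE = √(0.00752 + τ²).

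| τ (assumed) | SE | ± with z = 1.96 | ± with t, 2 df (4.303) |
|---|---|---|---|
| 0 | 0.087 | 17.0 points | 37.3 points |
| 0.05 | 0.100 | 19.6 points | 43.1 points |
| 0.10 | 0.132 | 25.9 points | 57.0 points |

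**The case against.** - **Scale.** The claim is exact for odds ratios only. On the probability scale a main-effects logit model can imply a changing gap. With White 50% and Black 30% in control, White 90% and Black 80% in intervention, and equal group sizes, the fitted gap moves from 19.7 to 10.3 points without an interaction. This is true, but the shift is fixed by the logit link and the two common odds ratios. It does not estimate a differential effect, and in Cases I and II it shows 10 points in both arms.
- **Intent.** The sample size sentence compares arms among Black children, so the team evidently means to look within that group, and the word adjusted may be loose. But no analysis matches that comparison, and a rise in Black uptake alone would not show a narrower gap, because White uptake could rise as much.
- **Model details.** The exact equality of fits assumes a random intercept and no covariate beyond race. Other covariates or race effects varying by practice would break the exact equality. They would not add a term for a change in the gap between arms.
- **Constructed examples.** The cases were built to share totals, so they show what is possible, not what is likely. The 500 is stated for Black children, while data will come from all eligible children, so the sampling term could be smaller than shown. The between-practice term would remain: with τ of 5 to 10 points, 4.303 × τ is already 22 to 43 points.
- **Little to gain.** This is a pilot. Respecting the north-south stratification would leave about 1 df (t = 12.706), and the SEs above would then give half-widths over 100 points. This stands, and it is why the contrast should be secondary and descriptive.

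**Conclusion.** The concern holds. The disparity sentence is wrong as written, not merely short of detail: a race main effect has no parameter for a change in the gap on the log-odds scale, and a larger sample would not supply one. In a random-intercept model with race as the only covariate, gaps that close, stay constant or open can give identical fits.

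That conclusion follows from the algebra and does not depend on the assumed White rates, race mix or practice counts. The precision figures do depend on those assumptions and on τ.

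The primary analysis of overall uptake is unaffected. The change should be made because this is the plan's only analysis of its main disparity measure, but the trial's primary conclusion does not rest on it.

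**What to change.** Keep the race-adjusted mixed model as the primary test of overall uptake. Replace the disparity sentence with:

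> A prespecified secondary mixed model will add an intervention-by-race/ethnicity interaction. From it we will report the intervention effect in Black and in Latino children, and the between-arm difference in the Black-White and Latino-White gaps in percentage points, each as an estimate with a 95% confidence interval that allows for four practices. These are pilot estimates, not powered tests. The covariate-adjusted overall effect will not be cited as evidence on disparity.

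The plan should also name the interval method before the data are seen, including whether the gap may vary by practice, the degrees of freedom, and how the location strata enter.

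The cost is one secondary model on data already being extracted; the primary outcome, test and sample size do not change. The downside is wide intervals with two practices per arm. The estimates can inform a larger trial but are unlikely to settle whether the gap changed.
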